Clinical outcomes	
 Proportion of progression free survival/time to progression (at intervals per standard of care). Proportion of objective response rate (at intervals per standard of care). Complete response defined as complete reduction of all visible disease; partial response defined as partial reduction in size of visible disease in some or all areas without any areas of increase in visible disease; stable disease defined as no change in overall size of visible disease, also including cases where some lesions increased in size and some lesions decreased in size; progressive disease defined as an increase in visible disease and/or presence of any new lesions, including cases where the clinician indicates progressive disease. Time to response (at intervals per standard of care), defined as the time to first response among patients who achieved complete response or partial response. Proportion of overall survival (1- and 2-years post-treatment initiation). 	Patient records

Variable	Operational Definition	Data Source(s)
All lab investigations + other investigations	
 All lab investigation conducted including complete blood count (CBC). 	Patient records
Quality of life	
 To be assessed via EORTC QLQ-C30 (Cancer Quality of Life Questionnaire). 	Patient questionnaire

BC = breast cancer; CBC = complete blood count; ECOG = Eastern Cooperative Oncology Group; EORTC QLQ-C30 = European Organization for the Research and Treatment of Cancer Quality of Life Questionnaire Core 30; MBC = metastatic breast cancer.

Table 2. Data Entry Schedule

Data Collection and Entry ¹ ►	Baseline	During Treatment with Palbociclib	Post Treatment with Palbociclib
	SOC Visit ¹	SOC Follow-up visits ² through End of Treatment with Palbociclib	SOC Follow-up Visits through End of Study ³
Informed Consent & Inclusion/Exclusion Criteria	x		
Patient Demographics, Medical History, Baseline Metastatic Disease Status	x		
BC Diagnosis and Recurrence History	x		
Comorbid conditions	x	x	
Concomitant Medications	x	x	
BC Treatment ⁴	x	x	x ⁵
Performance Status (ECOG)	x	x	
Clinical Outcomes ⁶	x	x	
Laboratory investigations, including CBC ⁷	x	x	
EORTC QLQ-C30 ⁸	x	x	

BC = breast cancer; SOC = standard of care; CBC = complete blood count; ECOG = Eastern Cooperative Oncology Group; EORTC QLQ-C30 = European Organization for the Research and Treatment of Cancer Quality of Life Questionnaire Core 30.

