3. ANALYSIS SETS/POPULATIONS

3.1. Full Analysis Set

The Full Analysis Set will contain all patients who fulfil the eligibility criteria. Date of enrollment is the date of Palbociclib treatment initiation (baseline).

Censoring rules: The maximum follow-up of a patient is 24 months. Patients will be censored at the end of Palbociclib treatment, or if the treatment continues, at 24 months. Other censoring events before 24 months are patient's withdrawal, disease progression or death, whichever occurs first. Patients' subsequent treatments after Palbociclib treatment discontinuation /disease progression will be recorded. Patients who are lost to follow-up will be censored at their last visit. For some clinical outcomes, different censoring rules will be applied as described in [Section 6.1](#), [Section 6.2](#), and [Section 6.3](#).

Data collection is estimated to start in Q2 2021 and it will end in Q4 2024.

Table and Figure Shells are presented in [ANNEX 2](#).

Patient inclusion and exclusion criteria are explained in [Section 2.1](#). Summary of patient enrolment per country and study site will be described as shown in [Table Shell 1](#).

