5. HANDLING OF MISSING VALUES

Should missing data occur, the data will be analysed as they are recorded in the eCRFs, and no imputation of missing data will be performed.

All data analysis in this study will be performed on the Full Analysis Set containing all patients who fulfil the eligibility criteria, and thus missing data is not used as criteria for excluding the patients from the data analysis. However, due to the nature of the study, there will likely be missing data for data elements, ie, data that are not documented in the patient's medical record.

For both categorical and continuous variables, the amount of missing data will be reported. For categorical variables, the missing values will be analysed in the descriptive summary tables as a category. The missing values in the continuous variables will be ignored when calculating the summary statistics of mean, median, standard deviation and quantiles. If some of the variables of interest show to have a large amount or proportion of missing data, the summary statistics of the variable should be interpreted accordingly.

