6.3. Analysis for the Exploratory Objectives

For the exploratory analyses, time to response (TTR), time to progression (TTP)/ progression free survival (PFS) will be studied and results will be presented as shown in [Table Shell 54](#). The stratified tables will be presented as in Table Shells [55-61](#).

TTR is defined as the length of time (in days) from the initiation of Palbociclib treatment until the first reported disease response (complete or partial).³⁴ Censoring rules presented in [Section 3.1](#) will be applied.

TTP is defined as the length of time (in days) from the initiation of Palbociclib treatment until the first reported disease progression.³⁴ Patients will be censored at the end of Palbociclib treatment, death, time of withdrawal, or end of the 24-month follow-up, whichever occurs first, at the respective time point. Specifically, death is not included in TTP but is considered as censoring event.

PFS is defined as the length of time (in days) from the initiation of Palbociclib treatment until the first reported disease progression or death due to any cause, whichever occurs first.³⁴ The disease progression will be considered at the first follow-up visit after the Palbociclib treatment initiation when the overall tumor response recorded is progressive disease. Patients with no disease progression documented will be censored at the last available medical record entry or end of the follow-up period. Patients who are lost to follow-up will be censored at their last visit.

Survival analyses will be used to estimate time to event endpoints TTR, TTP and PFS. The results of the survival analysis will be presented as the Kaplan-Meier survival curves and their 95% confidence intervals (CIs) that will be calculated using the log-log transformation of the survival probabilities.³⁶ Together with the Kaplan-Meier plots, the number of patients at risk at time intervals (eg, 90 days or as seen appropriate for the study) will be reported. [Figure Shells 1 and 2](#) show how time to response (TTR) and progression free survival (PFS) will be visualized as Kaplan-Meier plots including the number of patients at different time intervals. Kaplan-Meier plots can be presented by other categories (see [Section 3.2](#)), if enough data are available. Moreover, the results of the survival analysis will be reported as a descriptive summary table including the number of patients at risk, the number of patients

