Table Shell 54 - Descriptive summary table of the time to response, progression and progression free survival in Palbociclib treatment patients.

Variable	Summary statistics
Time to response (TTR)	
N at risk at the beginning	XX
N with event (response)	XX (xx%)
N censored	XX (xx%)
Q1 (95% CI)	xx.x (xx.x)
Median (95% CI)	xx.x (xx.x)
Q3 (95% CI)	xx.x (xx.x)
Min, max	XX.x, xx.,x
Missing	XX (xx%)
Time to progression (TTP)	
N at risk at the beginning	XX
N with event (disease progression)	XX (xx%)
N censored	XX (xx%)
Q1 (95% CI)	xx.x (xx.x)
Median (95% CI)	xx.x (xx.x)
Q3 (95% CI)	xx.x (xx.x)
Min, max	XX.x, xx.,x
Missing	XX (xx%)
Progression free survival (PFS)	
N at risk at the beginning	XX
N with event (disease progression)	XX (xx%)
N censored	XX (xx%)
Q1 (95% CI)	xx.x (xx.x)
Median (95% CI)	xx.x (xx.x)
Q3 (95% CI)	xx.x (xx.x)
Min, max	XX.x, xx.,x
Missing	XX (xx%)

Table Shell 55 - Descriptive summary table of the time to response, progression and progression free survival in Palbociclib treatment patients by treatment combination.

Variable	Combination therapy	
	Palbociclib plus letrozole/aromatase inhibitor	Palbociclib plus fulvestrant
Time to response (TTR)		
N at risk at the beginning	XX	XX
N with event (response)	XX (xx%)	XX (xx%)
N censored	XX (xx%)	XX (xx%)
Q1 (95% CI)	xx.x (xx.x)	xx.x (xx.x)
Median (95% CI)	xx.x (xx.x)	xx.x (xx.x)
Q3 (95% CI)	xx.x (xx.x)	xx.x (xx.x)
Min, max	XX.x, xx.,x	XX.x, xx.,x
Missing	XX (xx%)	XX (xx%)
Time to progression (TTP)		
N at risk at the beginning	XX	XX
N with event (disease progression)	XX (xx%)	XX (xx%)
N censored	XX (xx%)	XX (xx%)
Q1 (95% CI)	xx.x (xx.x)	xx.x (xx.x)
Median (95% CI)	xx.x (xx.x)	xx.x (xx.x)
Q3 (95% CI)	xx.x (xx.x)	xx.x (xx.x)
Min, max	XX.x, xx.,x	XX.x, xx.,x
Missing	XX (xx%)	XX (xx%)
Progression free survival (PFS)		
N at risk at the beginning	XX	XX
N with event (disease progression)	XX (xx%)	XX (xx%)
N censored	XX (xx%)	XX (xx%)
Q1 (95% CI)	xx.x (xx.x)	xx.x (xx.x)
Median (95% CI)	xx.x (xx.x)	xx.x (xx.x)
Q3 (95% CI)	xx.x (xx.x)	xx.x (xx.x)
Min, max	XX.x, xx.,x	XX.x, xx.,x
Missing	XX (xx%)	XX (xx%)

Table Shell 56 - Descriptive summary table of the time to response, progression and progression free survival in Palbociclib treatment patients by line of therapy.

Variable	Line of endocrine therapy	
	1 st	2 nd
Time to response (TTR)		
N at risk at the beginning	XX	XX
N with event (response)	XX (xx%)	XX (xx%)
N censored	XX (xx%)	XX (xx%)
Q1 (95% CI)	xx.x (xx.x)	xx.x (xx.x)

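### Time to response: the SAP replaces the protocol's responders-only definition with an all-patient Kaplan-Meier analysis that censors at progression, death and end of palbociclib, so its median describes neither responders nor the cohort

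*SAP*

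**What the plan says.** Protocol 8.3, Table 1, gives TTR as "defined as the time to first response among patients who achieved complete response or partial response". A patient who never responds has no TTR.

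SAP 6.3 says "TTR is defined as the length of time (in days) from the initiation of Palbociclib treatment until the first reported disease response", counting complete or partial response, and does not restrict the population. For censoring it says "Censoring rules presented in [Section 3.1](#) will be applied", and for the method "Survival analyses will be used to estimate time to event endpoints TTR, TTP and PFS", shown as Kaplan-Meier curves.

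SAP 3.1 supplies the rules: "Patients will be censored at the end of Palbociclib treatment, or if the treatment continues, at 24 months", and "Other censoring events before 24 months are patient's withdrawal, disease progression or death, whichever occurs first". SAP Section 5 fixes the population: "All data analysis in this study will be performed on the Full Analysis Set containing all patients who fulfil the eligibility criteria". Table Shell 54 gives TTR a row for the number at risk at the start, one for those with a response and one for those censored.

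SAP Annex 1, Table 3, has another version: time to first response starts at the first breast cancer diagnosis, not at the start of palbociclib.

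**The concern.** The two documents define different quantities under one name. The protocol asks how quickly responders respond. The SAP estimates time to response as if progression, death and stopping palbociclib were non-informative censoring, so that patients removed by these events would later have responded like those still at risk. For a response to palbociclib, those events end the opportunity. Kaplan-Meier then describes a population in which nobody progresses, dies or stops.

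At stake are Table Shells 54 to 61 and the TTR figure. Readers will probably take a median TTR as the time responders took, or as the time by which half the cohort had responded. The planned figure is neither.

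**Working it through.** **No figure to reproduce.** The documents give no TTR median, response curve or precision target.

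**Who is at risk.** The TTR sentence does not say all patients. That follows from the Full Analysis Set rule and from the Shell 54 row for censored patients: a responders-only TTR has nobody to censor.

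**Direction.** Take n patients with no withdrawals. At each response time Kaplan-Meier adds S(t-) x d/Y, where d is the number responding and Y the number at risk. The cumulative incidence adds d/n. The ratio, S(t-) x n/Y, starts at 1 and rises whenever a patient leaves by progression, death or end of treatment, because Y falls and S does not. Therefore:

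- 1-KM is never below the cumulative incidence, so the Kaplan-Meier median is never later than the cohort median.
- Later responses get more weight than earlier ones, so the Kaplan-Meier median is never earlier than the responders' median.

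No numerical assumption is used here.

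**Size, first model.** Response probability p is 60% (Protocol 6.1 cites a real-world study with 9.5% complete plus 50.5% partial response) or 50% (assumed). Responders' median TTR m is 3 or 5 months and non-responders' median time to leaving q is 6 or 10 months; both are assumptions without a source in the documents. Follow-up is 24 months (SAP 3.1).

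With a = ln2/m and b = ln2/q, the response hazard among those at risk is h(t) = p a e^(-at) / [p e^(-at) + (1-p) e^(-bt)]. Then 1-KM(24) = 1 - exp(-integral of h from 0 to 24), and the true cumulative response is p(1 - 2^(-24/m)).

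| p | m | q | KM median | Responders' median | 1-KM(24) | True response at 24 mo |
|---|---|---|---|---|---|---|
| 50% | 3 | 6 | 7.6 | 2.98 | 72% | 50% |
| 50% | 3 | 10 | 9.1 | 2.98 | 62% | 50% |
| 50% | 5 | 6 | 10.7 | 4.75 | 76% | 48% |
| 50% | 5 | 10 | 12.7 | 4.75 | 65% | 48% |
| 60% | 3 | 6 | 5.8 | 2.98 | 81% | 60% |
| 60% | 3 | 10 | 6.3 | 2.98 | 72% | 60% |
| 60% | 5 | 6 | 8.7 | 4.75 | 83% | 58% |
| 60% | 5 | 10 | 9.7 | 4.75 | 74% | 58% |

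At p = 60% the cohort median solves 0.6(1 - 2^(-t/m)) = 0.5, so t = m x log2(6) = 3 x 2.585 = 7.8 or 5 x 2.585 = 12.9 months. Kaplan-Meier gives 5.8-6.3 and 8.7-9.7, which is earlier. At p = 50% cumulative response stays just below half by month 24, so no cohort median exists, yet Kaplan-Meier prints 7.6 to 12.7 months.

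**Size, second model.** Constant hazards. The competing hazard is c = ln2/M, with M taken from median PFS values cited in Protocol 6.1: 9.5 months (fulvestrant combination), 20.2 and 24.8 months (letrozole combination). The response hazard r is solved from r/(r+c) x (1 - e^(-24(r+c))) = p. Example, p = 60%, M = 20.2: c = 0.0343 and r = 0.0663; check 0.0663/0.1006 x (1 - e^(-2.414)) = 0.60. Then 1-KM(24) = 1 - e^(-24 x 0.0663) = 79.6% and the KM median is ln2/r = 10.5 months.

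| p | M | 1-KM(24) | KM median | Cohort median | Responders' median |
|---|---|---|---|---|---|
| 60% | 24.8 | 76% | 11.5 | 15.0 | 6.6 |
| 60% | 20.2 | 80% | 10.5 | 14.1 | 6.0 |
| 60% | 9.5 | 93% | 6.1 | 9.3 | 3.7 |
| 40% | 24.8 | 53% | 22.2 | none | 8.1 |
| 40% | 9.5 | 72% | 13.1 | none | 5.1 |

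A simulation of 1,000 studies of 200 patients (p = 60%, M = 20.2) agrees: crude response 60.0%, 1-KM 79.6%, KM median 10.5 months, responders' median 6.1 months.

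**The case against.** Several points on the other side stand. Protocol 8.7 itself names Kaplan-Meier for response, so the method does not contradict the protocol; the conflict is over the population and the censoring of competing events. The same section lets the SAP modify the protocol and requires an amendment only for major changes to primary endpoints. TTR is exploratory, so this is an undeclared change, not a forbidden one. Shell 54 has no row for response by month 24, so the inflated proportion could only be read from the plot. The shell also prints the crude response percentage beside the median, which softens the harm.

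Two stronger readings are tempting and should not be made. First, a reader might infer that the Kaplan-Meier median is simply too long. It is longer than the responders' median, as any all-patient median would be; against the cohort's cumulative-incidence median it is too early. Second, a reader might cite disagreement between the TTR curve and the objective response rate in Table Shell 2 as evidence. SAP 6.2 counts stable disease in that rate and takes the last follow-up visit, while TTR uses the first complete or partial response. The two would differ under any estimator.

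**Conclusion.** The concern holds in this form: the SAP changes the TTR population without saying so and censors at competing events. The planned median lies between the responders' median and the cohort median, or is reported where no cohort median exists, and one minus the curve exceeds the actual cumulative complete or partial response. That direction is certain whenever such events precede later responses.

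The sizes are illustrative, because the documents give no rate of progression, death or stopping before response. The first model overstates 24-month response by 12 (62 - 50) to 28 (76 - 48) percentage points; the second by 13 (53 - 40) to 33 (93 - 60). Primary and secondary results are unaffected. It should be corrected before the tables are programmed.

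**What to change.** In SAP 6.3, Table Shells 54 to 61 and the TTR figure shell (numbered 2 in the Section 7 list and 1 in Annex 2), report TTR as the protocol defines it: median, quartiles and range among patients with complete or partial response. Drop the at-risk and censored rows for that summary.

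If an all-patient curve is wanted, replace one minus Kaplan-Meier by the Aalen-Johansen cumulative incidence of response. Treat progression, death and end of palbociclib as competing events, and censor only at withdrawal, loss to follow-up and month 24.

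In the same edit, change the Annex 1 definition so that the clock starts at palbociclib initiation, as in SAP 6.3. The cost is SAP wording and a standard SAS or R procedure. No new data are needed.

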2.1. Study Design

This is a prospective, non-interventional (NI), multicentre study being conducted in Africa Middle East (AfME) countries. The aim is to understand palbociclib treatment patterns, clinical outcomes and QoL of patients with metastatic/locally advanced BC being treated in routine clinical practice in seven AfME countries: Egypt, Jordan, Lebanon, UAE, Qatar, Morocco and KSA.

Participation in this study is not intended to change the routine treatment patients receive, as determined by their prescribing physicians; all treatment decisions, type and timing of the disease monitoring are per routine clinical care, and at the discretion of the treating physician and patient.

Study population

[figure not shown]
Patients with HR+/HER2- metastatic/locally advanced BC within Egypt, Jordan, Lebanon, UAE, Qatar, Morocco and KSA will be enrolled from a geographically representative population as well as from diverse treatment settings (eg, academic and community sites). Patients whose treatment decision with palbociclib combination has been made by their treating physician and meet the eligibility criteria will be invited to participate in the study in a consecutive manner and over 12 months of recruitment.

Approximately 350-410 patients from 19 centers across the seven countries will be enrolled. The recruitment period (ie, from first patient in to last patient in) will span over 12 months.

Patients will be enrolled at the time of treatment initiation with palbociclib, and will be followed up over a maximum of 24-month period at time intervals per routine care, or until the end of Palbociclib treatment, progression or patients' withdrawal from the study (whichever comes first). Eligibility will be assessed at the date of the enrollment.

Prospective data on clinical characteristics, treatments patterns, clinical outcomes and QoL will be collected in accordance with routine standard of care visits (Figure 1). Data will be collected at enrollment (time of treatment initiation), during treatment with Palbociclib (at time intervals per routine care) and after treatment with palbociclib. After the end of treatment with palbociclib, data related to the first immediate subsequent treatment received will be collected.

Figure 1. Study Design

FPI: first patient in; LPI: last patient in; LPO: last patient out; QoL: quality of life

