Endocrine sensitivity	Palbociclib treatment characteristics (secondary endpoint)	At Palbociclib treatment initiation	CRF sheet: Palbociclib Treatment Initiation	
Endocrine sensitivity will be reported in five categories:
 
 Endocrine therapy naïve Endocrine sensitive Primary endocrine resistant Secondary endocrine resistant Not applicable
Combination therapy	Stratification variable	At Palbociclib treatment initiation	CRF sheet: Palbociclib Treatment Initiation	
 Palbociclib plus letrozole/aromatase (Palbociclib and either Anastrozole, Letrozole or Exemastane) Palbociclib plus fulvestrant
Line of endocrine therapy	Stratification variable	At Palbociclib treatment initiation	CRF sheet: Palbociclib Treatment Initiation	
Palbociclib as first or second line endocrine therapy
 
 first line second line
Prior chemotherapy for advanced/metastatic disease	Palbociclib treatment characteristics (secondary endpoint)	At Palbociclib treatment initiation	CRF sheet: Palbociclib Treatment Initiation	
 Yes No
Schedule 3 weeks on, 1 week off	Palbociclib treatment	At Palbociclib treatment initiation	CRF sheet: Palbociclib	Palbociclib treatment schedule

PFIZER CONFIDENTIAL

CT24-WI-GL03-RF02 2.0 Non-Interventional Statistical Analysis Plan For Primary Data Collection Study 01-Jun-2020

Page 39 of 172

09017760990673e30A5481150 Palbociclib Read On: 28-Mar-2023 09:56 (GMT)

Variable	Role	Time point(s)	Data source(s)	Operational definition
	characteristics (secondary endpoint)		Treatment Initiation	
 • Yes • No
Reasons for different schedule	Palbociclib treatment characteristics (secondary endpoint)	At Palbociclib treatment initiation At follow-up visits	CRF sheet: Palbociclib Treatment Initiation, Palbociclib Treatment Cycle Form	Reason for treatment schedule different from 3 weeks on, 1 week off 
 • To avoid toxicity • Due to line of therapy received • ECOG performance score • Age • Presence of comorbidities • Patient request • Metastases status • Stage at advanced breast cancer diagnosis • Concomitant medications • Other
Cycle interrupted	Palbociclib treatment characteristics (secondary endpoint)	At follow-up visits	Palbociclib Treatment Cycle Form	
 • Yes • No

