Treatment completed	Palbociclib treatment characteristics (secondary endpoint)	At Palbociclib treatment discontinuation	CRF sheet: Palbociclib treatment discontinuation form	
 Yes (reason of discontinuation is "Completion of planned course of treatment"); no (other reason or censored)
Duration of Palbociclib treatment	Palbociclib treatment characteristics (secondary endpoint)	At Palbociclib treatment discontinuation	CRF sheet: Palbociclib treatment discontinuation form	
 Time (in days) from first to last day in Palbociclib treatment
Another treatment after discontinuing treatment with Palbociclib	Palbociclib treatment characteristics (secondary endpoint)	At Palbociclib treatment discontinuation	CRF sheet: Palbociclib treatment discontinuation form	
 Yes No
Reason for end of follow-up	Clinical outcomes (primary endpoint)	At last visit	CRF sheet: End of Observation/ End of Study Follow Up	
End of follow-up will be categorised as:
 
 Death Patient withdrawal Lost to follow-up End of 24-months follow-up period
Concomitant medications	Clinical characteristics (secondary endpoint)	At Palbociclib treatment initiation, At follow-up visits	CRF sheet: Concomitant Medications Form	Open field. 10 most common will be listed.
Supportive therapies	Supportive therapies (secondary endpoint)	At the initiation of Palbociclib treatment	CRF sheet: Supportive Therapies Form	The type of the supportive therapies received by the patients since the BC diagnosis. Open field. 10 most common will be listed.
Comorbidities	Clinical characteristics (secondary endpoint)	At the initiation of Palbociclib treatment	CRF sheet: Comorbidities form	Open field. 10 most common comorbidities will be listed
Proportion of progression free patients	Clinical outcomes (primary endpoint)	At the follow-up visits	CRF sheet: Tumor Assessment Form and End of follow-up	The proportion of the patients who are alive and for whom no progression of the disease has been reported.
Progression free survival (PFS)	Clinical outcomes (exploratory endpoint)	At the follow-up visits	CRF sheet: Tumor Assessment Form and End of follow-up	The time from the Palbociclib treatment initiation until the progression of the disease or death to any cause, whichever occurs first.

PFIZER CONFIDENTIAL

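### SAP 6.3 stops TTP, but not PFS, at the end of palbociclib; a progression recorded after that date counts in PFS and is censored in TTP, so TTP is liable to be overstated

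*SAP*

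**What the plan says.** SAP 6.3 defines both endpoints from palbociclib initiation but stops them differently.

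- **TTP:** "Patients will be censored at the end of Palbociclib treatment, death, time of withdrawal, or end of the 24-month follow-up, whichever occurs first". The section then says explicitly that death is a censoring event for TTP.
- **PFS:** the event is time "until the first reported disease progression or death due to any cause, whichever occurs first". For censoring: "Patients with no disease progression documented will be censored at the last available medical record entry or end of the follow-up period". The end of palbociclib is not mentioned.

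SAP 3.1 sets a general default, "Patients will be censored at the end of Palbociclib treatment, or if the treatment continues, at 24 months", but lets later sections override it: "For some clinical outcomes, different censoring rules will be applied as described in" Sections 6.1, 6.2 and 6.3. PFS therefore follows 6.3.

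SAP 6.1 and 6.3 date progression at the follow-up visit where the overall response is recorded as progressive disease. SAP Annex 1 Table 3 lists disease progression among the reasons for discontinuing palbociclib. The only dating of treatment end there is in the treatment-duration variable, "Time (in days) from first to last day in Palbociclib treatment". That entry is not linked to censoring.

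**The concern.** The protocol pairs TTP and PFS in one exploratory objective, and SAP Table Shells 54 to 61 print them together. A reader will expect them to differ only in how death is treated, which is the one difference the SAP explains. The second difference, at the end of treatment, is not explained.

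That difference matters because stopping palbociclib is often a consequence of progression. If the recording visit falls after the end-of-treatment date, the progression that ended treatment is removed from the TTP event count and replaced by a censoring time shortly before it. Kaplan-Meier then treats the patient as having the same future risk as those still under observation.

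The published tables would not reveal this. In Shell 54 the event row is labelled as disease progression for both TTP and PFS, and PFS deaths are not shown separately. Lost progressions cannot be told apart from deaths.

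**Working it through.** The plan gives no figure for TTP or for the effect of its censoring rule, so there is nothing to reproduce. The check has three parts.

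**1. The two rules applied to one patient.** Treatment ends on day d; progressive disease is recorded at a visit on day d + k, with k > 0, before 24 months. Under the PFS rule progression is documented, so this is an event on day d + k. Under the TTP rule end of treatment comes first, so the patient is censored on day d.

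**2. Effect of a share f of progressions dated just after treatment end.** These patients leave the risk set almost when they would have had the event, so the risk set is nearly unchanged while the observed hazard falls to (1 − f) times the true one. Kaplan-Meier then estimates S(t)^(1 − f).

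Inputs, all cited in protocol 6.1: 18-month PFS 51.6% (US chart review, first-line palbociclib plus letrozole); median PFS 24.8 months (first-line phase III trial); median PFS 9.5 months (phase III trial with fulvestrant). For the two medians, times are taken as exponential with λ = ln 2 / median. These PFS rates include deaths and stand in for progression alone. The share f is an assumption.

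| Base rate | f = 0 | 10% | 25% | 50% |
|---|---|---|---|---|
| 18 months, S = 0.516 | 51.6% | 0.516^0.9 = 55.1% | 0.516^0.75 = 60.9% | 0.516^0.5 = 71.8% |
| 24 months, median 24.8 | 51.1% | 54.7% | 60.5% | 71.5% |
| 12 months, median 9.5 | 41.7% | 45.5% | 51.9% | 64.5% |

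For scale, with 200 patients the standard error at 51.6% is √(0.516 × 0.484 / 200) = 3.5 points if nobody is censored earlier. A simulation of 400,000 patients with no deaths and median 24.8 months, placing the last dose 0 to 1 month before the progression visit, gave 54.6%, 60.3% and 71.3% at 24 months for f = 10%, 25% and 50%. This agrees with the closed form.

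**3. Stopping that progression does not trigger.** Same simulation base, with an assumed 15% per year stopping:

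| Hazard after stopping | 24 months, no censoring at stop | 24 months, TTP rule | Difference |
|---|---|---|---|
| unchanged | 51.1% | 51.1% | none |
| × 2 | 47.1% | 51.1% | +4.0 points |
| × 3 | 44.4% | 51.1% | +6.7 points |
| × 0.5 | 53.9% | 51.1% | −2.8 points |

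The rule is harmless only if stopping carries no information about progression.

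**The case against.** **Many stops are not progression.** Annex 1 also lists toxicity, patient decision, poor adherence and physical status. Part 3 shows no bias, or even a reversed one, for such stops. A reader might infer that TTP is simply overstated; the documents support only that it is liable to be. Overstatement remains the likelier direction because progression is a listed stopping reason.

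**The end-of-treatment date is undefined.** The duration variable refers to the last day in treatment, not the last dose. With "Schedule 3 weeks on, 1 week off" as the reference schedule, the off week can be read as part of treatment. It is therefore tempting to set f at 7/28 = 25%, but that assumes evenly spread visits and off-week days counted as post-treatment, neither of which is stated. The ordering clause also ranks only the censoring reasons and gives no tie rule for progression found at discontinuation. This stands: f cannot be fixed from the documents.

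**Progression after treatment may not be recorded.** SAP 2.1 follows patients "or until the end of Palbociclib treatment, progression or" withdrawal, and SAP Table 1 and protocol Table 2 have no post-treatment mark for clinical outcomes. On that reading the two rules largely coincide. Against it, protocol 8.2 continues data collection after palbociclib over 24 months, footnotes 2 and 3 to SAP Table 1 require outcome data at every follow-up visit and data entry after treatment, and the Annex 1 reasons for end of follow-up do not include end of treatment. The conflict is real. The core case, however, needs only the visit that records the progression behind the stop, not long later follow-up.

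**An on-treatment TTP is legitimate.** It is, and it matches the SAP 3.1 default. It would still need a rule keeping the progression that ended treatment as an event.

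**Two further inferences are not supported.** A reader might put the TTP-PFS gap mainly down to dating, but TTP lies above PFS by definition because deaths are censored, and deaths without progression were not modelled. A reader might also expect the rule to leave the TTP median or upper quartile unreached. That depends on extrapolation: a Weibull through 75.5% at 12 months and 51.6% at 18 (shape 2.11, scale 21.9 months) gives exp(−(24/21.9)^2.11) = 29.7% at 24 months. The upper quartile is then unreached even with f = 0, and the median only once f exceeds about 43%. Under an exponential with median 24.8 months, the median is unreached by 24 months regardless.

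**Conclusion.** The point holds in a limited form. SAP 6.3 gives TTP and PFS different stopping rules without a reason, and a progression documented after the end of palbociclib counts in one and not the other. This follows from a stated rule. The likely effect is informative censoring that overstates TTP: at a true 18-month rate of 51.6%, by about 3, 9 or 20 points for f = 10%, 25% or 50%. Those figures assume that f is constant over time, that such progressions are recorded, and that the cited PFS rate is a fair stand-in. TTP is exploratory and nothing is tested, so the consequence is a misleading description, not a wrong decision.

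Two neighbouring defects should be settled together with this one. Annex 1 defines TTP differently from 6.3, starting at the first breast cancer diagnosis and counting death from the disease. And 6.1 gives the primary progression-free proportion no censoring rule of its own, so the 3.1 default, including censoring at end of palbociclib, may reach a primary endpoint.

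**What to change.** 1. In SAP 6.3, remove the end of palbociclib from the TTP censoring list. Use one progression date and one censoring rule for TTP and PFS, with death (censored in TTP, an event in PFS) as the only difference.
2. If an on-treatment TTP is intended instead, define the end-of-treatment date, count as an event any progression recorded up to and including the end-of-treatment assessment, and censor the others at their last on-treatment tumour assessment.
3. Reconcile SAP 2.1 and the marks in SAP Table 1 and protocol Table 2 with protocol 8.2, SAP Table 1 footnotes 2 and 3, and the Annex 1 end-of-follow-up reasons, so that it is clear whether progression is recorded after treatment.
4. Align the Annex 1 TTP definition with 6.3.
5. Give 6.1 its own censoring rule, or state that the end-of-palbociclib default does not apply to the primary progression-free proportion.

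The cost is a few sentences in the SAP plus the reconciliation in item 3. Under item 1, TTP is no longer strictly on-treatment and relies on whatever progression data are recorded after treatment. Item 2 removes the core bias even if longer post-treatment outcomes are not collected.
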